7.1.1. Sensitivity Analysis

Sensitivity analyses include:

- Percent change from baseline in plasma oxalate (Cohort A) or pre-dialysis plasma oxalate (Cohort B) values to Month 6 by cohorts in Safety Analysis Sets

The sensitivity analyses performed will be similar to that described for the primary analysis above but conducted using the Safety Analysis Set, of which the MMRM models include those patients who have no plasma oxalate assessment Month 3 or beyond.

7.2. Subgroup Analysis

Subgroup analyses will include analyses of primary endpoints by age groups and weight-based dosing groups defined according to the baseline values:

Age group: <2 years, 2 to <6 years, 6 to <18 years, \geq 18 years

Weight-based dosing category: <10 kg, 10 to <20 kg, and \geq 20 kg.

Other subgroups (eg, eGFR for Cohort A) may be examined, if deemed appropriate. Some subgroups (eg, age) may be collapsed due to the small number of subjects in each category.

Subgroup descriptive statistical analysis (N, mean, standard error, median, min, max) will be conducted for primary analysis of percent change from baseline in plasma oxalate (Cohort A) / pre-dialysis plasma oxalate (Cohort B) summarized through Month 6 in Full Analysis Set.

The subgroup analyses may be performed for secondary endpoints in Section 7.3.

7.3. Secondary Endpoints

For secondary efficacy endpoints, Full Analysis Set will be used; for secondary PK endpoints, the PK Analysis Set will be used.

All secondary efficacy endpoints will be analyzed and reported with by-patient listings and by-patient figures of actual values, change from baseline and percent change (where appropriate per endpoint) at each visit. Tabular summaries using descriptive statistics (N, mean, standard error, median, min, max) will be reported. For binary endpoints, the number and percentages of patients in each category will be displayed at each visit. Other analyses may be generated if applicable.

7.3.1. Percent Change from Baseline to Month 6 in Plasma Oxalate AUC between Dialysis Sessions

The objective of the AUC analysis in Cohort B is to evaluate the effect of lumasiran on the change from baseline in plasma oxalate AUC for a patient between dialysis sessions. The plasma oxalate profile assessment consists of an overnight visit requiring collection of up to 8 blood samples for plasma oxalate over the course of a 24-hour span. The plasma oxalate AUC will be measured during screening to establish baseline, Month 3, and Month 6 in the Primary Analysis Period, and at Month 12, Month 36, and Month 48 during the Long-term Extension Period.

For patients in Cohort B, a secondary endpoint of percent change from baseline in plasma oxalate AUC(0-24h) will be summarized at Month 6. Plasma oxalate AUC(0-24h) is defined as

the plasma oxalate area under the curve of the 24 hour window after the pre-dialysis assessment. The AUC(0-24h) plasma oxalate assessment for a patient visit will be considered valid only if both of the following criteria are met:

- Results are available from at least the four key sampling collection timepoints (specifically, pre-dialysis ($t = 0$), 30 minutes before the end of dialysis ($t \sim 4$ hr), 4 hours postdose ($t \sim 8$ hr), and 24 hours post dialysis ($t \sim 24$ hr));
- The number of days since last dialysis session for a given post-baseline profile is the same as the number of days since last dialysis session during the screening period.

AUC(0-24h) will be calculated using plasma oxalate results with the linear-trapezoidal method using actual collection times relative to pre-dialysis sampling time. An exact 24h assessment for the purpose of calculating the AUC(0-24h) will be calculated using linear interpolation or extrapolation on the two non-missing scheduled assessments closest to the 24-hour timepoint.

Plasma oxalate profiles will be compared across visits within patients. LS mean percent change from baseline plasma oxalate AUC(0-24h) at Month 6 and its associated 95% confidence interval will be estimated using MMRM model including data evaluated at Month 3 and Month 6. Additionally, the AUC(0-24h) parameter will be listed and descriptively summarized by study visit. The Full Analysis Set will be used for this analysis. A similar approach as used for the primary analysis will apply, in case when the model fails to converge.

Additionally, AUC(4-24h) will be similarly analyzed. AUC(4-24h) is defined as the plasma oxalate area under the curve of the 20 hour window from the end of dialysis (30 minutes before the end of dialysis assessment) until the next dialysis session (24h timepoint). This approach is intended to reduce the variability introduced by different dialysis parameters between patients. The percent change from baseline in plasma oxalate AUC(4-24h) will be summarized through Month 6 in a similar manner to the percent change from baseline in plasma oxalate AUC(0-24h) as a sensitivity analysis to the secondary endpoint. The pre-dialysis scheduled assessment will not be required for a valid AUC or utilized in this assessment, otherwise this analysis will remain consistent with methodology to assess the percent change from baseline in plasma oxalate AUC(0-24h).

7.3.2. Change from baseline to Month 6 in other Plasma and Urinary Oxalate Parameters

The analyses for the following secondary endpoints will also be performed using a restricted maximum likelihood based Mixed-effect Model Repeated Measures approach.

- Absolute change from baseline to Month 6 in plasma oxalate during the Primary Analysis Period
- Percent change and absolute change from baseline to Month 6 in 24-hr urinary oxalate corrected for BSA during the Primary Analysis Period
- Percent change and absolute change in spot urinary oxalate: creatinine ratio during the Primary Analysis Period

[figure not shown]
Analysis by cohort will include evaluable assessments through Month 6, which will be modeled with fixed effects of scheduled visits and baseline covariate of corresponding assessment,

including patient as a random factor. LS mean of an endpoint of Month 3 to Month 6, averaged over these timepoints will be presented along with corresponding SEMs and 95% CIs. The autoregressive (1) covariance structure matrix will be used to model the within-patient error given the small sample size for this study. Similar approach as used for the primary analysis will apply, in case when the model fails to converge.

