7.2.1. Populations to be Analyzed

The populations (analysis sets) are defined as follows:

- Safety Analysis Set: All patients who received any amount of lumasiran during the study.

- Efficacy Analysis Set: All patients who received any amount of lumasiran and have at least 1 valid plasma oxalate value at baseline and at the Month 3 assessment or beyond.
- PK Analysis Set: All patients who received any amount of lumasiran have at least 1 postdose blood sample for PK parameters and have evaluable PK data.

The primary population used to evaluate efficacy will be the Efficacy Analysis Set and safety will be the Safety Analysis Set. The PK Analysis Sets will be used to conduct PK analyses.

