4. PATIENT POPULATION

4.1. Patient Definitions

The populations (analysis sets) are defined as follows:

- Safety Analysis Set: All patients who received any amount of lumasiran during study.
- Full Analysis Set: All patients who received any amount of lumasiran and have at least one evaluable plasma oxalate value (pre-dialysis in Cohort B) at baseline and at least one evaluable plasma oxalate value from assessment(s) at Month 3 through Month 6
- PK Analysis Set: All patients who received any amount of lumasiran, have at least 1 postdose blood sample for PK parameters, and have evaluable PK data.

The Safety Analysis Set will be used for safety analyses and the sensitivity analysis of efficacy. The Full Analysis Set will be used to evaluate efficacy endpoints. The PK Analysis Sets will be used to conduct PK analyses.

This study will consist of 2 periods: a 6-month Primary Analysis Period followed by a long-term (54 months) extension period. The Primary Analysis Period starts at the first date/time of lumasiran dose administration and ends at either the date/time of lumasiran dose administration at Month 6 (exception being that Month 6 assessments (eg, plasma oxalate and PK assessments) which occur after the Month 6 dose will be included) or the date of the Month 6 visit (Day 169) for patients who discontinued treatment prematurely. Primary analysis will be conducted using the Primary Analysis Period data collected through 6 months.

The Long-term Extension Period, starts at the date/time of lumasiran dose administration at Month 6 and is through the end of the study. Analysis of the Long-term Extension Period will focus on long-term efficacy and safety effects of lumasiran.

Patients who discontinue from study drug during the 6-month Primary Analysis Period (defined above) will be encouraged to remain on the study and complete assessments (including plasma oxalate but excluding PK assessments) through Month 6. They will also be asked to complete safety follow-up visits, once every 3 months, per the safety follow-up schedule for up to 12 months after the last dose of lumasiran.

Patients who discontinue study drug after Month 6 will be asked to return for their next scheduled visit to complete early termination (ET) assessments and complete safety follow-up visits, once every 3 months, per the safety follow-up schedule for up to 12 months after the last dose of lumasiran.

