5. GENERAL STATISTICAL METHODS

5.1. Sample Size Justification

The planned enrollment for the study is 20 patients, including at least 6 patients in each cohort.

Of those 20 patients, the planned enrollment includes at least 4 patients <6 years of age at consent, and at least 2 patients between ≥ 6 to <18 years of age at consent.

The sample size was determined based on feasibility considerations, not power calculations.

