5.5. Missing Data

Patients who discontinue the study treatment prior to Month 6 will be encouraged to remain on study and complete their remaining clinical visits (excluding PK assessments) through the visit at

Month 6 and only safety follow-up visits afterwards. All data collected regardless of whether it was collected before or after treatment discontinuation will be used for efficacy analysis. However, it is possible that data will remain missing.

Plasma oxalate AUC(0-24h) is considered missing if a plasma sample from any of the four, key collection timepoints (ie, pre-dialysis, 30 minutes before the end of dialysis, 4 hours postdose, and 24 hours post dialysis) is missing. Linear interpolation or extrapolation may be applied to determine the availability of values for these timepoints, if appropriate. For calculation of an AUC for plasma oxalate profile, details are provided in Section 7.3.

For safety analyses, no date will be assigned to any AEs with fully missing dates or partially missing dates. An AE will be considered treatment emergent unless it can be unequivocally determined (from the partial onset date and/or a partial or complete stop date) that the event occurred prior to the first dose of lumasiran.

For medications with partial start or stop dates: the first day/month will be imputed for start date, and the last day/month will be imputed for stop date. For medications with a completely missing start date, the medications will be considered as started prior to the first dose of study drug in this study; medications will be classified as prior or both prior and concomitant depending on the medication stop dates. If any medications have a completely missing stop date, then the medication will be assumed as ongoing.

For partial dates of renal stone events (start and stop dates): the first day/month will be imputed for start date, and the last day/month will be imputed for stop date. It is not expected that renal stone dates will be completely missing.

Due to blood sample volume limitations related to patient age/size, missing data in blood sample tests are expected.

The following are considerations for the evaluability of plasma oxalate due to potential post-dose dialysis treatments in Cohort A.

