- If a Cohort A patient has at least one plasma oxalate value during Months 3-6 with intervening transient dialysis (<=2 weeks), then the patient's plasma oxalate values that are prior to dialysis and at least 48 hours after the end of the last dialysis session are evaluable and will be included in primary analysis.
- If a patient has at least one plasma oxalate value during Months 3-6 before long-term (>2 weeks) dialysis, then:
 - The patient's plasma oxalate values before the start of dialysis are evaluable and will be included in the primary analysis
 - The patient's plasma oxalate values after the dialysis are unevaluable and will be excluded from the primary analysis
- If a Cohort A patient begins long-term (>2 weeks) dialysis between baseline and Month 3, then the patient's plasma oxalate values post dialysis are unevaluable. Hence, the patient will be excluded from primary analysis for Cohort A and only included in sensitivity analysis

- If a Cohort A patient begins transient (≤ 2 weeks) dialysis between baseline and Month 3, then:
 - Data collected during the patient's dialysis and recovery period (48 hours) are unevaluable and will be set as missing and be excluded from the primary analysis
 - The remainder of the patient's data including baseline to Month 6 are evaluable and will be used in the primary analysis

The following are considerations for the evaluability of plasma oxalate due to potential dialysis modification (clinically significant change in dialysis prescription as assessed by investigator, e.g., frequency or access modality such as catheter to AV fistula) in Cohort B.

- If a Cohort B patient's dialysis is modified for at least 4 weeks after the Month 3 assessment, plasma oxalate collected before dialysis modification are evaluable and will be included in the primary analysis. Data collected after the dialysis modification will be censored.
- If a Cohort B patient's dialysis is modified for at least 4 weeks prior to the Month 3 assessment, patient data after modification of dialysis are considered unevaluable. Hence, the patient will not be included in primary analysis, but will be included in safety analysis set for the sensitivity analysis.

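### Endpoints that do not depend on plasma oxalate are analysed in a set defined by Month 3–6 plasma oxalate evaluability, so sustained dialysis events before Month 3 remove treated patients from their tables

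*SAP*

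**What the plan says.** **Membership.** SAP 4.1 admits to the Full Analysis Set (FAS) treated patients with an evaluable baseline plasma oxalate and "at least one evaluable plasma oxalate value from assessment(s) at Month 3 through Month 6". Protocol 7.2.1 defines its Efficacy Analysis Set more loosely. Treated patients must "have at least 1 valid plasma oxalate value at baseline and at the Month 3 assessment or beyond", with no upper limit at Month 6 and no dialysis rule.

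**Evaluability.** SAP 5.5 makes plasma oxalate unevaluable after a Cohort A patient begins dialysis lasting more than 2 weeks between baseline and Month 3: "Hence, the patient will be excluded from primary analysis for Cohort A and only included in sensitivity analysis". For Cohort B, values after a dialysis modification of at least 4 weeks before the Month 3 assessment are treated in the same way. Shorter episodes cost only the affected values and a 48-hour recovery period.

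**Use of the set.** SAP 4.1: "The Full Analysis Set will be used to evaluate efficacy endpoints". SAP 7.3: "For secondary efficacy endpoints, Full Analysis Set will be used". SAP 7.4 applies the FAS to exploratory efficacy endpoints in both study periods unless otherwise noted, and 7.4.1 names it for cardiac oxalosis at Month 6.

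**Sensitivity analysis.** SAP 7.1.1 repeats one analysis in the Safety Analysis Set: percent change in plasma oxalate.

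**The concern.** Starting dialysis, or changing its prescription, is a good reason not to read a later plasma oxalate value as a drug effect. It is not in itself a reason to leave out a quality-of-life score, an echocardiogram or a developmental assessment. Because one membership rule serves all efficacy endpoints, a reason specific to plasma oxalate becomes a reason to remove the patient from everything else.

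The removal depends on what happens after the first dose. In Cohort A it selects against patients whose kidney function failed within about three months. Such patients may also be replaced (Protocol 4.3.4). They stay in the study and keep being assessed: Protocol 3.1 moves them to Cohort B, and Protocol 6.4 continues their sampling. Data from up to 54 months of extension could therefore be collected and then left out of the efficacy tables. With no control arm, nothing in the tables would show the selection.

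**Working it through.** **Step 1. Apply the membership rule to each case in SAP 5.5.**

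| Event | Evaluable Month 3–6 value? | In FAS? |
|---|---|---|
| Cohort A, dialysis ≤2 weeks before Month 3 | Yes, outside dialysis and 48 h recovery | Yes |
| Cohort A, dialysis >2 weeks starting before Month 3 | No | **No** |
| Cohort A, dialysis >2 weeks after at least one Month 3–6 value | Yes, the earlier value(s) | Yes |
| Cohort B, modification <4 weeks | Yes, if another Month 3–6 value is evaluable | Yes, on that condition |
| Cohort B, modification ≥4 weeks before Month 3 | No | **No** |
| Cohort B, modification ≥4 weeks after Month 3 | Yes, the earlier value(s) | Yes |

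**Step 2. Identify the endpoints affected.** In the visible text these are urinary oxalate (7.3.2), quality of life (7.3.3 and 7.4.3), cardiac oxalosis at Month 6 (7.4.1) and developmental milestones (7.4.2). Renal stones, nephrocalcinosis and the other oxalosis measures are secondary endpoints of the extension period (SAP 3.2). The general sentence in 7.3 reaches them without exception, but the text of 7.3.4 is redacted, so a different set there cannot be ruled out. None of these endpoints has a visible sensitivity analysis in a wider set.

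**Step 3. Size.** There is no planned precision to reproduce: "The sample size was determined based on feasibility considerations, not power calculations". The cohort sizes follow from "The planned enrollment for the study is 20 patients, including at least 6 patients in each cohort", which allows 6 to 14 per cohort. The documents give no expected rate of these events, so one or two excluded patients per cohort is an assumption.

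- Share lost = k/n. Half-width of a one-sample 95% CI in SD units = t(0.975, n−1)/√n.
- For n = 6: 2.571/√6 = 1.049. For n = 5: 2.776/√5 = 1.242. The ratio is 1.183.

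| Cohort n | Excluded k | Share lost | Half-width, all n | Half-width, n−k | Increase |
|---|---|---|---|---|---|
| 6 | 1 | 16.7% | 1.049 | 1.242 | 18.3% |
| 6 | 2 | 33.3% | 1.049 | 1.591 | 51.6% |
| 10 | 1 | 10.0% | 0.715 | 0.769 | 7.5% |
| 10 | 2 | 20.0% | 0.715 | 0.836 | 16.9% |
| 14 | 1 | 7.1% | 0.577 | 0.604 | 4.7% |
| 14 | 2 | 14.3% | 0.577 | 0.635 | 10.0% |

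The half-widths are for a simple mean, not for the repeated-measures model.

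- Shift in a mean when one patient is left out = (that patient − mean of the others)/n. In a cohort of 6 this is one sixth of the gap.
- For a binary endpoint in a cohort of 6, if the excluded patient has the only event, 1/6 (16.7%) becomes 0/5.

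**Step 4. Compare with the protocol.** The protocol's set would admit a patient whose first valid value came after Month 6, and a patient with valid Month 3–6 values taken on dialysis. The SAP's set admits neither. SAP Section 1 says changes to protocol methods will be described in Section 8. The only analysis-set change listed there is the PK set.

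**The case against.** Several stronger readings are tempting, and the documents do not support them.

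- **That any dialysis start or regimen change before Month 3 removes the patient.** Only dialysis of more than 2 weeks in Cohort A, or a modification of at least 4 weeks in Cohort B, does so.
- **That eGFR results are lost.** eGFR is an efficacy endpoint only in Cohort A and only in the extension (SAP 3.2), and it is sampled only off dialysis (Protocol 6.3.4). A patient on continuing dialysis from before Month 3 has no extension eGFR in any set. eGFR also appears in the laboratory shift tables (SAP 7.6.3), which use the Safety Analysis Set.
- **That growth is lost.** Height, weight and BMI z-scores are also summarised under Vital Signs (SAP 7.6.4).
- **That the data disappear.** SAP 5.2 lists all CRF data, and Protocol 7.2.5.1 promises listings and figures for early crossovers. In cohorts this small, listings are informative.
- **That results must look too favourable.** This is plausible for Cohort A but not shown. In Cohort B a qualifying modification includes a move from catheter to fistula, which need not mark a worse patient.
- **That small children will drop out through blood-volume limits.** All four scheduled values, at Months 3, 4, 5 and 6, would have to be missing, and a blood-draw priority list exists (Protocol 6.5.5.4).

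Cases should also be few. Patients expected to start dialysis within 6 months are excluded (Protocol 4.2), and elective regimen changes are barred through Month 6 (Protocol 6.5.5.5).

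Two further objections carry weight. A patient with a pre-dialysis baseline and on-dialysis outcomes raises a real question of interpretation, and the plan reports by cohort, so any wider set must say where that patient is counted. The SAP's sentence "All data collected regardless of whether it was collected before or after treatment discontinuation will be used for efficacy analysis" concerns stopping study drug. It shows a general preference for keeping data but does not settle what to do after dialysis starts.

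These points limit how far the problem reaches. They do not explain why plasma oxalate evaluability should decide entry to a quality-of-life or echocardiogram table.

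**Conclusion.** The concern holds in limited form. As written, a patient with a sustained dialysis event before Month 3 is dropped from the FAS tables and models for urinary oxalate, quality of life, cardiac oxalosis at Month 6 and development. The general rule would extend this to stones, nephrocalcinosis and the other oxalosis measures unless the redacted text says otherwise.

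One such patient is between 7% (of 14) and 17% (of 6) of a cohort. If 20 enrol, at least one cohort has 10 or more, so 17% applies to at most one of the two. The number of such patients is unknown and probably small. That the exclusion depends on a post-treatment event is certain from the text; that it flatters the results is a reasonable inference, not a finding.

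Separately, the narrowing of the protocol's analysis set is not declared in SAP Section 8. That omission stands whatever the number of patients affected.

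**What to change.** 1. In SAP 7.3 and 7.4, analyse efficacy endpoints not based on plasma oxalate in all treated patients with a baseline and at least one post-baseline value of that endpoint. Summarise by cohort at enrolment, with crossover patients flagged. If the sponsor prefers to keep the FAS as the main set, add at minimum a Safety Analysis Set summary for these endpoints.
2. Keep the Month 3–6 evaluability rule for plasma oxalate level and plasma oxalate AUC only.
3. Add to SAP Section 8, with a reason, the change from the protocol's Efficacy Analysis Set (a valid value at Month 3 or later) to the FAS (an evaluable value within Months 3–6).

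The cost is SAP wording and different denominators in some tables, with no new data collection. The downsides are that N will differ between endpoints, that results may be slightly less favourable, and that crossover patients will contribute on-dialysis outcomes against a pre-dialysis baseline. The flag makes that last point visible.

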5.6. Visit Windows

For tabular and graphical summaries, all data will be tabulated and analyzed per the evaluation visit as recorded on the electronic case report forms (eCRF) even if the assessment is outside of window.

Unless otherwise specified, data collected at an unscheduled visit will be included in by-patient listings and/or spaghetti plot figures, but no assignment of the scheduled visit will be made for the purposes of summary tabulations. However, unscheduled study visits will be used in the calculation of baseline values if prior to first dosing and for any categorical shift tables (eg shift from baseline to worst post-baseline value).

The following are time windows for the analysis of Plasma Oxalate Profile samples in Cohort B:

Blood Collection Sampling time	Window
Pre-Dialysis	Prior to dialysis on the same day as the dialysis
30 minutes before end of dialysis	from 1 hour prior to end of dialysis through the end of dialysis
30 minutes post-dialysis	after the end of dialysis through 1 hour post-dialysis
2 hours post-dialysis	>1 hour post-dialysis through 3 hours post-dialysis
4 hours post-dialysis	>3 hours post-dialysis through 6 hours post dialysis
8 hours post-dialysis	>6 hours post-dialysis through 10 hours post-dialysis
12 hours post-dialysis	>10 hours post-dialysis through 16 hours post-dialysis
24 hours post-dialysis	>18 hours post-dialysis through pre-dialysis the next day (if dialysis session scheduled day after current dialysis) or 29 hours post-dialysis (if no dialysis session scheduled day after current dialysis)

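### The 20-hour window of AUC(4-24h) is nominal: its start and end points do not enforce it, and a profile without a pre-dialysis sample has no stated time origin

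*SAP*

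**What the plan says.** The Cohort B secondary endpoint is the percent change in plasma oxalate AUC(0-24h). SAP 7.3.1 computes it "with the linear-trapezoidal method using actual collection times relative to pre-dialysis sampling time" and obtains an exact 24 h value by linear interpolation or extrapolation. AUC(4-24h) is a sensitivity analysis of that endpoint, meant to lessen between-patient variability that comes from dialysis parameters.

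SAP 7.3.1 describes the AUC(4-24h) window in these ways:

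- By length: "AUC(4-24h) is defined as the plasma oxalate area under the curve of the 20 hour window from the end of dialysis".
- By anchors: "30 minutes before the end of dialysis assessment) until the next dialysis session (24h timepoint".
- By nominal times, in the list of key samples: "30 minutes before the end of dialysis ($t \sim 4$ hr" and "24 hours post dialysis ($t \sim 24$ hr".

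On the pre-dialysis sample it says: "The pre-dialysis scheduled assessment will not be required for a valid AUC or utilized in this assessment". In every other respect the AUC(0-24h) method carries over.

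SAP 5.6 sets the accepted sample times. The pre-dialysis sample counts if taken "Prior to dialysis on the same day as the dialysis". The start sample may fall anywhere in the last hour of dialysis. The last sample may fall from more than 18 h after dialysis up to the next day's session, or up to 29 h if there is none.

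**The concern.** The length, the anchors and the clock agree only when the start sample falls exactly 4 h after the pre-dialysis sample. The SAP standardises the 24 h end but gives no matching rule for an exact 4 h start. Both the pre-dialysis sample and the start sample can move between two visits of one patient, and the area moves with them.

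The clock itself can also be absent. SAP 5.5 and 7.3.1 treat AUC(0-24h) as missing when the pre-dialysis sample is missing. With the other validity rules carried over, the profiles that AUC(4-24h) admits in addition are those that lack this sample. They are also the ones with no stated zero from which to find 24 h.

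At stake is whether this analysis is a steadier check on AUC(0-24h) than AUC(0-24h) itself. SAP 5.1 plans at least 6 patients in Cohort B, so a single mistimed profile counts.

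**Working it through.** **1. The plan's own figure.** From the nominal times in SAP 7.3.1, 24 - 4 = 20 h. This reproduces the stated length. It implies a session of 4 + 0.5 = 4.5 h with the pre-dialysis sample at its start.

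**2. Window length under the carried-over clock.** Length = 24 - (time from pre-dialysis sample to start sample). If the pre-dialysis sample is at session start and the start sample is 0.5 h before the end of a session of D hours, length = 24.5 - D. Session lengths are assumed; the documents give none.

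| Case | Length at nominal start sample | Over the accepted last hour |
|---|---|---|
| D = 3 h | 21.5 h | 21 to 22 h |
| D = 4 h | 20.5 h | 20 to 21 h |
| D = 4.5 h | 20.0 h | 19.5 to 20.5 h |
| D = 6 h | 18.5 h | 18 to 19 h |
| D = 4.5 h, pre-dialysis sample 2 h before session | 24 - 6 = 18.0 h | 17.5 to 18.5 h |

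**3. Effect of moving the pre-dialysis sample, no true effect.** Assumed profile: 100 before dialysis, 35 at the start sample (t = 4 h), then a rebound at 0.12 per h that reaches 100 at 24 h:

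c(t) = 35 + A(1 - exp(-0.12(t - 4))), with A = 65/(1 - exp(-2.4)) = 71.48.

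Area over L hours from the start sample = (35 + A)L - A(1 - exp(-0.12L))/0.12. AUC(0-24h) adds the trapezoid (100 + 35)/2 = 67.5 times the gap from the pre-dialysis to the start sample.

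| Pre-dialysis sample | L | AUC(4-24h) | Change | AUC(0-24h) | Change |
|---|---|---|---|---|---|
| Reference | 20 h | 1588 | | 1588 + 67.5×4 = 1858 | |
| 1 h earlier | 19 h | 1488 | -6.3% | 1488 + 67.5×5 = 1826 | -1.7% |
| 2 h earlier | 18 h | 1390 | -12.5% | 1390 + 67.5×6 = 1795 | -3.4% |

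AUC(0-24h) loses area at the end but gains some at the front, because its total length stays 24 h. AUC(4-24h) only loses. Divided by window length, the same shifts give -1.3% and -2.8%.

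**4. Other assumed profiles.** Nine profiles were tried: end-of-dialysis level 25%, 35% or 50% of the pre-dialysis level, and rebound 0.05, 0.08 or 0.15 per h. Areas were linear-trapezoidal on the scheduled samples. The 1 h shift gave -6.8% to -5.8% and the 2 h shift -13.6% to -11.6%. Moving only the start sample within its accepted hour gave -2.0% to +2.2%.

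**5. Pre-dialysis sample missing.** If the actual last sample closes the window, SAP 5.6 allows 18 + 0 = 18 h up to 29 + 1 = 30 h, and a literal 24 h after dialysis gives 24 + 0.5 = 24.5 h. Against a 20 h reference with no true effect, the nine profiles gave about -10% to -9% with the last sample at 18 h after dialysis, and +26% to +32% at 24 h.

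**6. Session length.** With the same session length and timing at both visits (3 to 6 h tried), a true -30% came back as -30.0%. It cancels.

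**7. Candidate fixes, true change -30%.** The shifts were: start sample at either end of its hour, session of 4 or 5.5 h against 4.5 h, and pre-dialysis sample 2 h early.

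| Rule | Range of estimates |
|---|---|
| As written | -39.5% to -27.6% |
| Area divided by actual duration | -32.8% to -29.0% |
| Fixed 18 h window from end of dialysis | -30.1% to -29.9% |

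**The case against.** A reader might infer that the result depends on how long each patient's session is. The documents do not support that as a general claim. The endpoint is a within-patient percent change, so a stable length cancels, and Protocol 6.5.5.5 bars elective changes in session duration through Month 6. What remains is a medically indicated change, or the profiles after Month 6.

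A reader might also infer that the analysis defeats its own purpose. SAP 7.3.1 promises less than that: to lessen variability between patients, without naming sample timing and without claiming to eliminate anything. Nor is the window length unstated; it is stated and not enforced.

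The notes to Protocol Table 6 limit the timing scenario. In the first 6 months pre-dialysis samples, including those in profiles, are to be taken 24 h (±2 h) or 48 h (±4 h) after the previous session, and timing relative to dialysis is to stay consistent. An arbitrary early draw is therefore not planned conduct. But the rule ties the sample to the previous session, not to the start of the current one, and SAP 5.6 would still accept an early sample.

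Finally, the exact 24 h rule is written for AUC(0-24h), so AUC(4-24h) could be read as ending at the actual last sample. SAP 5.6 times that sample from the end of dialysis, so no origin would be missing. This is a fair reading, but the carry-over clause points the other way, and on this reading the window runs from 18 to 30 h. Neither reading fixes 20 h.

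**Conclusion.** The point stands as a minor one. AUC(4-24h) has a nominal 20 h window that its anchors do not enforce, and under the carried-over method a profile without the pre-dialysis sample has no stated origin. Because the area is not scaled by duration, a 1 h or 2 h earlier pre-dialysis sample at one visit moves that patient's percent change by -6.3% or -12.5% with no true effect. That is more than three times the movement in the endpoint it checks (6.3/1.7 = 3.7; 12.5/3.4 = 3.7). One post-baseline profile off by 12.5 points would move a simple mean of six patients by 12.5/6 = 2.1 points.

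The percentages rest on assumed oxalate profiles and session lengths. The window lengths follow from the SAP's sampling rules plus the assumed sessions.

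A reader might infer that the flaw could create or hide a drug effect. The material does not show this: moving a cohort mean by that much would need similar shifts in the same direction across patients, and in the tests with the origin known (working, step 7) a true -30% stayed between -39.5% and -27.6%. The primary endpoint is unaffected, and AUC(0-24h) keeps its fixed 24 h window.

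**What to change.** In SAP 7.3.1, for AUC(4-24h):

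1. Measure time from the recorded end of the dialysis session instead of the pre-dialysis sample. SAP 5.6 already times the post-dialysis samples from that point.
2. Integrate over a fixed window from that origin, the same at baseline and post-baseline, with interpolation at both ends. The 18 h used in the check is one example; SAP 5.6 accepts the last sample only beyond 18 h after dialysis, so that end point could be interpolated. Otherwise, divide the area by its actual duration before computing the percent change. The fixed window was the steadier of the two in the check.
3. Reconcile the 20-hour length, the end point at the next session, and the label "24 hours post dialysis ($t \sim 24$ hr" with that definition. A sample 24 h after a 4.5 h session that began at t = 0 would be at t = 28.5 h, not 24 h. Cover patients with no session the next day.

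The cost is a few lines of SAP text and a small change to the derivation code, with no new data. The downside is a slightly shorter window, or an average concentration in place of an area.
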